## 4.2 INCLUSION CRITERIA

Indication for aortic endovascular stent graft repair as determined by the treating physician.

The patient is / has:

- Age 55 or more at the time of informed consent signature.
- Non-ruptured infra-renal AAA that requires treatment, and in the opinion of the Investigator, whose anatomy is adequate to receive or has already received the GORE® EXCLUDER® Conformable AAA Endoprosthesis **with ACTIVE CONTROL System** (EXCC device).

Protocol version 3.1, dated: 11/11/2021

Favourable opinion given by South East Scotland Research Ethics Committee 01 on 12/01/2021

- An Informed Consent Form dated and signed by the Subject either before *or* within 30 days of EXCC device implantation

### **4.3 EXCLUSION CRITERIA**

The patient is / has:

- Previous infra-renal aortic surgery prior to the implantation of the EXCC device
- Been treated in another aortic or thoracic medical device study within 1 year of study enrollment.
- Active infection
- Penetrating aortic ulcer or dissection or intramural haematoma in the treated segment
- Any clinically significant medical condition, which in the opinion of the investigator, may interfere with the study results or reduce life expectancy to <2 years
- In the opinion of the investigator unable or unwilling to comply with the requirements of the study.

### **4.4 WITHDRAWAL CRITERIA**

A Participant may withdraw from observational data collection at any time and should notify the participating site in this event. It is important to encourage patients to return for both follow-up visits. The local PI may also withdraw the Participant from the study at any time based on his / her medical judgment.

## 5. ADVERSE EVENTS AND REPORTING PROCEDURES

### 5.1 RELATED AND ANTICIPATED ADVERSE EVENTS

Patients with AAA undergoing EVAR have the potential risks of treatment and complications that are known to be associated with endograft implantation. Competent, experienced medical/surgical staff will perform all procedures and every effort will be made to prevent adverse events. The adverse events listed below are anticipated procedure-related risks:

Anticipated risks that do not need expedited reporting		
Access vessel dissection or rupture	Graft migration	Respiratory failure
Amputation	Graft limb	Spinal cord ischaemia
Aortic rupture	thrombosis/stenosis/occlusion	Stroke
Buttock claudication	Haemorrhage	UTI
Chest infection	Limb ischaemia	Visceral ischaemia
Endoleak	Multiple organ failure	Wound infection
Graft infection	Myocardial infarction	
Graft kinking	Renal failure	

**Risk-to-Benefit Rationale:** As this is an **observational study of real-world routine clinical practice**, there are **no additional** benefits or **risks dependent upon participation** in the registry.

### 5.2 SERIOUS ADVERSE EVENTS

#### 5.2.1 Serious Adverse Event ISO 14155 Definition

Serious Adverse Events (SAE) are defined as those adverse events that

- leads to death
- leads to serious deterioration in the health of the participant that either results in
- a life-threatening illness or injury, or
- a permanent impairment of a body structure or body function, or
- in-patient or prolonged hospitalization, or
- medical or surgical intervention to prevent life threatening illness or injury or permanent impairment to a body structure or a body function

### 5.2.2 Serious Adverse Event (SAE) Relationship to device, procedure or disease

Each reported SAE will be assessed by the local Principal Investigator for its primary suspected relationship to the device, procedure, disease and patient co-morbidity, as per the definitions given below. Given this is an observational registry and the endograft implantation is part of patient's routine treatment for their AAA (i.e. **not** a research procedure), only **related and unexpected** SAEs (i.e. those not listed in section 5.1) will be reported on the SAE form.

#### Study Device-related

The functioning or characteristics of the device caused or contributed to the SAE.

#### Study Procedure-related

The procedure (and not the device) caused or significantly contributed to the SAE.

#### Disease-related

The SAE was a result of the underlying AAA progression for which the study procedure is being performed, and not the device or procedure.

#### Not-related

A SAE which cannot be attributed to the device, procedure, or AAA. These will *not* be captured.

### 5.2.3 SAE Reporting Procedures

- As above, only those SAEs that have been assessed as **related** (to the disease, device and/or implantation technique) **and** that are **unexpected** (i.e. those not listed in section 5.1) will be reported using the Serious Adverse Event Form, which will also be documented in the participant's permanent medical record.
- The following information on each reported Serious Adverse Event will be collected:
  - Description and, if possible, diagnosis\*
  - Onset Date
  - Relationship

- Classification
- Severity
- Frequency
- Treatment
- Outcome
- Resolution Date

\* If unable to provide a diagnosis, report the symptoms as separate events.

- The local Principal Investigator at each Site is ultimately responsible for reporting **related and unexpected SAEs** to the Chief Investigator, and must do so immediately or within 24 hours of being made aware of the event. Local PI should also report this to the endograft manufacturer through normal product surveillance mechanisms.

**Chief Investigator contact details for reporting SAEs**  
**[contact], attention [name]**  
**Please mark "URGENT"**  
**[contact] (Mon to Fri 09.00 – 17.00)**

- **Death**, including cause of death, must always be reported on the SAE form.
- The initial report can be made verbally but must be promptly followed with a detailed, written report on the study SAE form provided in the BSET-CLEVAR CRF Booklet.
- The local PI should ensure that follow-up information is provided when available. Where supporting documents are sent with this form, these must be anonymised. Where the information available is incomplete at that time, as much information as can be ascertained should be sent to ensure timely reporting, with additional information provided as soon as it is known. Additional information received for an event (follow-up or corrections to the original event data) needs to be detailed on a new Serious Adverse Event Reporting Form.
- Reports of **related and unexpected SAEs** should be reported to the Sponsor and to the South East Scotland Research Ethics Committee 01 within 15 days of the Chief Investigator

becoming aware of the event using the NRES SAE form for non-IMP studies. The Chief Investigator must also notify all local PIs at participating centres.

- Serious Adverse Events with an outcome status of “Ongoing” should be assessed at each follow-up evaluation to determine if the event has resolved. Serious Adverse Events ongoing at study completion / discontinuation should be left as “Ongoing” on the SAE case report form.

## 6. ASSESSMENT AND FOLLOW-UP

### 6.1 SCHEDULE OF EVENTS

	Screening/ Baseline	Prior to procedure	Procedure	Discharge	1 st follow-up (4 weeks to 3 months post-op)	2 nd follow-up (12 months ± 4 weeks post- op)
Informed Consent (option to recruit before or within 30 days of procedure)	X	X		X	X (within 30 days only)	
Demographics and Medical History	X #	X #				
Physical Examination	X #	X #		X		
Blood results	X #	X #				
ASA risk classification & operative details			X			
SAE assessment (related and unexpected events only)				X	X	X
CT Scan+	X				X	X *
Duplex Ultrasound+						X *

\* 12 months follow-up imaging type (CT or duplex) will be at the discretion of the implanting site.

# Demographics & Medical history information, physical examination and blood test results are all standard of care procedures prior to EVAR (i.e. no extra tests or procedures solely for the study) and they can either be obtained during screening assessment **or** at a subsequent routine appointment at the Vascular Out-Patients clinic prior to endograft implantation.

+Pre-op CT scan before EVAR and post-op CT and/or duplex ultrasound after EVAR are standard of care imaging investigations; BSET-CLEVAR Registry will only collect and evaluate these routine imaging data and the study does not involve any additional imaging investigations.

## 6.2 PRE-PROCEDURE EVALUATIONS

The following evaluations, which are *standard of care before undergoing EVAR*, must be completed **prior to** treatment of the patient by GORE® EXCLUDER® Conformable AAA Endoprosthesis with ACTIVE CONTROL System:

- Demographics
- Medical history
- Physical examination
- Chemistry
- Haematology
- APTT
- Serum Creatinine
- CT

## 6.3 PROCEDURE

The Sponsor and the funder will not impose requirements that limit health care professionals from exercising their best medical judgment for treatment. Therefore, patient selection, diagnostic imaging and treatment interventions will be determined by physicians based on clinical practice standards. No specifications for device use, indication, follow-up schedule or requisite data collection outside of the site's routine practice will be required.

Patients who meet the BSET-CLEVAR registry inclusion Criteria and are treated with the Gore Conformable AAA Endoprosthesis with ACTIVE CONTROL System at participating sites will be considered enrolled in the BSET-CLEVAR registry once they sign the study-specific informed consent form, either *before* or *within 30 days* of device implantation.

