**Secondary endpoints**

- Technical success, defined as successful access and deployment of all required EXCC Device components
- In-hospital mortality
- Adjuncts to deal with type 1 endoleak at primary procedure
- Freedom from Type 1 or 3 endoleak at end of procedure, by 3\* months and around 1\* year
- 1-year aneurysm-related re-intervention rates
- 1-year aneurysm-related mortality

**POPULATION** Up to 200 patients presenting with abdominal aortic aneurysm (AAA) to the study centres (up to 30 NHS hospitals affiliated to BSET in the United Kingdom)

**ELIGIBILITY** Patients with AAA who are suitable for endovascular repair of their AAA and are either being considered for or have received treatment by endoprosthesis implantation

**DURATION** Approximately 38 months, including 12-month follow-up

\* Timelines for the first and final follow-up are flexible: First follow-up, including CT scan imaging, may be carried out between 4 weeks and 3 months and second (final) follow-up, including either a CT scan or duplex U/S imaging (depending on local EVAR surveillance policy), may be done at 12 months ± 4 weeks.

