## **3. STUDY DESIGN**

### **3.1 DESCRIPTION OF STUDY DESIGN**

The study is a prospective multicenter observational cohort registry of patients treated with the GORE® EXCLUDER® Conformable AAA Endoprosthesis with ACTIVE CONTROL System in the UK. Recruitment will take place in up to 30 experienced UK centers with extensive EVAR experience and implanted five or more GORE endoprosthesis. Up to 200 patients will be recruited and followed up for 1-year. It is anticipated recruitment will be complete in ~2 years and that the study will run for ~ 3 years. The maximum number of subjects enrolled per site is 30. All screened patients will have been previously evaluated in a standard manner (as part of their routine care) for their anatomical suitability for EVAR with CT (see section 4.1 for further details on patient identification and screening assessment). All patients will undergo post-operative CT between 4 weeks and 3-months post implantation in line with routine local surveillance policies following EVAR and further follow-up to 1-year will be at the discretion of the implanting center.

Patients may be enrolled into the study provided all inclusion and no exclusion criteria are met as specified in Section 4. Procedural details may vary between sites, but all will follow standard hospital

Protocol version 3.1, dated: 11/11/2021

Favourable opinion given by South East Scotland Research Ethics Committee 01 on 12/01/2021

protocol for EVAR and patient care management. Subjects will be evaluated through hospital discharge and return for follow-up visits between 4 weeks and 3 months and at 12 months  $\pm$  4 weeks.

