### **Secondary Endpoints**

- Technical success defined as successful access and deployment of all required EXCC Device components
- In hospital mortality
- Adjuncts to deal with type 1 endoleak at surgery
- Freedom from Type 1 or 3 endoleak at end of procedure, 3 months and 1 year
- One-year aneurysm-related re-intervention rates
- One-year aneurysm-related mortality

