## **4. PARTICIPANT ENTRY**

### **4.1 IDENTIFICATION AND SCREENING**

The target patient population for the GORE® EXCLUDER® Conformable AAA Endoprosthesis with ACTIVE CONTROL System registry is a consecutive series of patients who undergo endovascular

treatment for abdominal aortic aneurysm. Prior to study-specific screening, all patients will have had a CT scan as part of their routine care and they will have been identified for routine treatment of their AAA by EVAR after meeting accepted surgical threshold criteria. These patients will then be screened for potential inclusion in the BSET-CLEVAR registry by review of their medical notes by vascular clinicians from the patient's existing clinical care team at the participating hospital or during the vascular multidisciplinary team (MDT) meeting, or in person during a routine appointment at the Vascular Out-patients clinic. If deemed suitable, the patient will be provided with study-specific patient information sheet (PIS) by their Vascular Surgeon or Vascular Specialist Nurse, either in person during a routine appointment (in which case they will be given a minimum of 24 hours to consider participating in the registry), or by post prior to their routine appointment/hospital visit. If the latter, the PIS will be sent to the potential Participant in pre-paid envelopes (provided by the study co-ordinating centre) before the patient's routine vascular out-patients appointment or hospital admission, so that the patient will have had time to read the information before they visit the hospital. They will have opportunity to discuss the information contained in the PIS with their Vascular Surgeon/Vascular Specialist nurse and asked to consider participating in the registry.

Written consent will be obtained from those patients who agree to participate either before *or* after their operation and they will be assigned a study ID number. If written consent is being obtained after EVAR, this will be done within 30 days of implantation. Only patients who meet all of the inclusion criteria and none of the exclusion criteria specified below will be enrolled. At each participating hospital, a log of all screened patients will be kept locally, which will record basic demographic data (patient initials/year of birth/sex; to ensure patients have not been recorded in duplicate) and reasons for non-eligibility.

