### **9.2 CONSENT**

Consent to enter the study must be sought from each Participant only after a full explanation has been given, an information leaflet offered and time allowed for consideration (minimum 24 hours). The formal consent of a Participant using the approved consent form, must be obtained by the local PI (or designated colleague detailed in the delegation log) before EVAR or within 30 days of EVAR and study data must not be collected until informed consent has been obtained. . The consent form will be signed and personally dated by the Participant or legally authorized representative, and the person who conducted the informed consent discussion. The original signed informed consent form will be retained in the Participant's hospital records. A copy of the informed consent document will be given to the Participant for his or her records, and an additional copy filed in the Participant's study file. Consent of vulnerable patients should be obtained in line with local hospital policy

The right of the Participant to refuse to participate without giving reasons must be respected. After the Participant has entered the study the clinician remains free to give alternative treatment to that specified in the protocol at any stage if he/she feels it is in the Participant's best interest, but the reasons for doing so should be recorded. In these cases the Participant remains in the study for the purposes of follow-up and data analysis. All Participants are free to withdraw at any time from the protocol treatment without giving reasons and without prejudicing further treatment. In addition, any significant, new information which emerges while the study is in progress that may influence a Participant's willingness to continue to take part in the study will be provided to the Participant.

The local PI shall verify that documentation of the acquisition of informed consent is recorded in each Participant's records in accordance with applicable regulations.

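### The protocol conflicts with itself on whether attempted but failed EXCC implants are enrolled, and the treated-only reading biases technical success upward

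*Protocol*

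**What the plan says.** Some passages describe a cohort of treated patients:

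- Section 3.1: "The study is a prospective multicenter observational cohort registry of patients treated with the GORE® EXCLUDER® Conformable AAA Endoprosthesis".
- Section 6.3: patients who satisfy the inclusion criteria and "are treated with the Gore Conformable AAA Endoprosthesis with ACTIVE CONTROL System at participating sites will be considered enrolled" when they have signed consent, before or up to 30 days after implantation.
- Section 8.2 counts the sample in patient implants. Section 8.3 names one analysis population, the whole 200-patient registry, and no set of attempted implants.
- Section 4.1, on late consent: "If written consent is being obtained after EVAR, this will be done within 30 days of implantation". Sections 4.2 and 6.3 start the window at the same point.

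Other passages are wider:

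- Study Summary, Eligibility: patients suitable for endovascular repair who "are either being considered for or have received treatment by endoprosthesis implantation".
- Section 4.2: a patient "whose anatomy is adequate to receive or has already received the GORE® EXCLUDER® Conformable AAA Endoprosthesis". The first alternative needs no implant.
- Section 4.1: the target "is a consecutive series of patients who undergo endovascular" treatment, with consent before or after the operation and a study ID assigned to those who consent.
- Section 9.2, on participants given another treatment after entry: "In these cases the Participant remains in the study for the purposes of follow-up and data analysis".

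The endpoint concerned is in section 3.2: "Technical success defined as successful access and deployment of all required EXCC Device components".

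**The concern.** The endpoint has two ways to fail: access is not achieved, or not every required component is deployed. A patient whose access fails, or whose EXCC implant is abandoned before anything is placed, has not been treated with the device. If treatment with the device is a condition of enrolment, the denominator omits a class of failures that the endpoint is defined to count. The reported rate would then be too high, and the same patients would be missing from in-hospital mortality.

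Analysis cannot repair this afterwards. Section 9.2 bars collection of study data before consent, so a patient who is never enrolled leaves no outcome data. The local screening log in section 4.1 holds basic demographics and reasons for non-eligibility, not attempted implants. With up to 30 centres and wording that can be read two ways, sites may also apply different rules.

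**Working it through.** **Plan's own figure.** The only derived count is the number expected to complete, in section 8.2: 200 × 0.90 = 180 and 200 × 0.95 = 190. This reproduces the stated 180 to 190. The protocol gives no technical success rate, so the size of the bias has to rest on assumptions.

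**Who is in, by route and outcome of the attempt**

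| Consent | Attempt | Section 6.3 read literally | Summary, 4.2 and 9.2 |
|---|---|---|---|
| Before surgery | All components deployed | In, success | In, success |
| Before surgery | Some components deployed | In, failure | In, failure |
| Before surgery | Nothing implanted | Out | Can be in, failure |
| After surgery | All components deployed | In, success | In, success |
| After surgery | Some components deployed | In, failure | In, failure |
| After surgery | Nothing implanted | Out | Out in effect |

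The third row is the contradiction. The last row does not depend on which reading is chosen: the part of section 4.2 written for late entrants requires that the device has been received, and without an implant the 30-day window in 4.1, 4.2 and 6.3 has no starting date. Successes can therefore be recruited before or after surgery, but non-implants at best only before.

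**Size of the bias.** Assumed inputs, none of them in the documents:

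- f: true failure rate among attempts, 1% to 5%
- a: share of failures in which nothing is implanted
- q: share of those non-implants still counted through consent before surgery

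Observed success = (1 − f) / [(1 − f) + f(1 − a) + f·a·q]

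Example with f = 3%, a = 0.5, q = 0: 0.97 / (0.97 + 0.015) = 98.5%, against a true 97.0%, a bias of 1.5 points.

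Observed success on the treated-only reading (q = 0):

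| True failure f | True success | a = 1 | a = 0.5 | a = 0 |
|---|---|---|---|---|
| 1% | 99% | 100% | 99.5% | 99% |
| 2% | 98% | 100% | 99.0% | 98% |
| 3% | 97% | 100% | 98.5% | 97% |
| 5% | 95% | 100% | 97.4% | 95% |

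The bias is 1 to 5 points for a = 1, about 0.5 to 2.4 points for a = 0.5, and zero for a = 0. With a = 1, the attempts missing per 200 enrolled are 200f/(1 − f), about 2 at f = 1% and 10.5 at f = 5%. If consent before surgery captures half of the non-implants (q = 0.5, a = 1), the bias is again 0.5 to 2.4 points. With every attempt counted (q = 1) it is zero.

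**Against sampling error.** The exact 95% interval is 98.17% to 100% for 200/200 and 94.96% to 99.45% for 196/200. If the true rate were 98% and all failures were non-implants, the interval around the observed 100% would exclude the truth.

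**The case against.** A reader might infer that failed attempts never enter the denominator and that technical success is close to 100% by construction. The documents do not support that. Consent may be taken before surgery, section 4.2 accepts anatomy that is merely adequate to receive the device, the Study Summary admits patients under consideration, and section 9.2 can keep those switched to another treatment. Nor is treatment with the device defined as complete deployment. Section 1.2 describes a multi-component system, so a patient who receives the trunk but lacks another required component is treated, enrolled and a failure. The 100% column needs every failure to be a non-implant, for which there is no evidence here.

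It can also be said that section 9.2 applies only after a participant has entered the study. If section 6.3 keeps non-implanted patients from entering, 9.2 never reaches them and the two do not clash directly. That is fair, and is why 9.2 is only a possible part of the conflict. The conflict with section 4.2 and the Study Summary remains.

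Further, a registry of treated patients is an openly declared design, and a rate conditional on treatment can be interpreted if labelled as such. Technical success is one of six secondary endpoints, reported descriptively, with no target or comparator. The primary endpoint, neck coverage on CT, needs an implanted graft and is unaffected. All of this stands and lowers the weight of the point. It does not explain why an endpoint that counts access should be measured in a cohort that may exclude access failures.

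Finally, endpoint-specific denominators are commonly set in an SAP, and section 8.3 promises one. An SAP can choose among enrolled patients; it cannot restore those the enrolment rule left out.

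**Conclusion.** The point holds as a contradiction with a known direction of bias and an unknown size. Section 6.3, with 3.1 and 8.2, conflicts with the Study Summary, section 4.2 and possibly 9.2 on whether attempted but failed implants are enrolled. On the treated-only reading, and on any reading for patients consented after surgery, access failures and abandoned implants are omitted and technical success is overstated.

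The range of 0 to 5 points rests on assumed failure rates of 1% to 5%, on the assumed share of failures with no implant, and on how many of those patients consented beforehand. Because the endpoint is secondary and descriptive, the point should be corrected but does not threaten the main result of the study.

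**What to change.** 1. In sections 6.3 and 8.3, define the population for technical success and in-hospital mortality as every consented patient in whom EXCC implantation was attempted. Count an attempt that ends without an implant as a technical failure.
2. In sections 4.1, 4.2 and 6.3, time late consent from the procedure (the attempted EXCC implantation) rather than from implantation. Sections 6.1 and 9.2 already count from the procedure or from EVAR. In 4.2, widen the condition for late entrants from receipt of the device to an attempt to implant it; otherwise failed attempts approached after surgery remain ineligible.
3. Log at each site the attempts that end without an implant, for example as an entry in the existing screening log, so that the number not consented is known.
4. Restrict only the CT neck-coverage endpoint to implanted patients.
5. Reconcile section 9.2 with 6.3, so that both say the same about participants given another treatment, and align the Study Summary and sections 3.1 and 8.2.

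The cost is a short amendment, a few extra participants with a brief CRF, and a slightly lower reported success rate. No change to clinical management is involved.
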